13. TRIAL COMMITTEES

The Steering Committee

The trial is overseen by a Steering Committee made up of the principal grant holders, [name] (Dundee), [name] and [name] (Oxford), and [name] (Aberdeen), together with [name] (London), [name] (Oxford), [name] (Aberdeen) and a representative from each participating centre. Meetings will be held annually, and the chair will alternate between [name] and [name]. The Steering Committee will take responsibility for any major decisions, such as the need to close recruitment early to one or more parts of the study or to change the protocol for any reason.

The Project Management Group

The trial is co-ordinated by its Project Management Group. This consists of the principal grant holders, [name] (Dundee), [name] [name] (Oxford), and [name] (Aberdeen), together with [name] (London) and [name] (Aberdeen) and those employed to work on the trial in the co-ordinating centres. Observers may be invited to attend at the discretion of the Project Management Group. This group will meet at four monthly intervals. Again, the chair will alternate between [name] and [name].

The Data Monitoring Committee

A data monitoring committee will be established, independent of the trial organisers. The committee will consist of three members (one of whom will act as chairman): an orthopaedic surgeon who is not involved in the trial; a clinician with experience of trials; and a statistician with experience of monitoring accumulating trial data.

During the period of recruitment to the trial, interim analyses will be supplied, in strict confidence, to the data monitoring committee, together with any other analyses that the committee may request. This may include analyses of data from other comparable trials. In the light of these interim analyses, the data monitoring committee will advise the Steering Committee if, in its view, one or more of the randomised comparisons in the trial has provided both (a) proof beyond reasonable doubt that for all or some types of patients one particular type of prosthesis is clearly indicated or contraindicated¹, and (b) evidence that might reasonably be expected to influence materially the care of people who require knee replacement by clinicians who know the results of this and comparable trials. The Steering Committee can then decide whether or not to modify intake to the trial or to report results early. Unless this happens, however, the steering committee, project management group, clinical collaborators, and trial staff (except those who supply the confidential analyses) will remain ignorant of the interim results considered by the committee.

The frequency of interim analyses will depend on the judgement of the chairman of the committee, in consultation with the Steering Committee.

14. FINANCE

The trial is supported by a grant from the Health Technology Assessment Programme of the NHS Executive Research and Development Programme with supplementary funding from the major manufacturers of knee prostheses in the UK.

Note:

¹ Appropriate criteria for proof beyond reasonable doubt cannot be specified precisely. A difference of at least three standard deviations in the interim analysis of a major endpoint may be needed to justify halting, or modifying, such a study prematurely. If this criteria were to be adopted, it would have the practical advantage that the exact number of interim analyses would be of little importance, and so no fixed schedule is proposed (Peto R et al *Br J Cancer* 1976; **34**: 584-612).

15. SATELLITE STUDIES

The funds provided by the NHS R&D HTA Programme are to conduct the main trial as described in this protocol. Nevertheless, it is recognised that the value of the KAT trial will be enhanced by smaller ancillary studies of specific aspects. Plans for such studies should, however, be discussed and agreed in advance with the Project Management Group.

16. PUBLICATION

The success of the trial depends entirely on the wholehearted collaboration of a large number of doctors and nurses. For this reason, chief credit for the trial will be given, not to the committees or central organisers, but to all those who have wholeheartedly collaborated in the trial. The trial's publication policy is described in detail in Appendix 7. The results of the trial will be reported first to trial collaborators. The main report will be drafted by the Trial Management Group, and the final version will be agreed by the Steering Committee before submission for publication, on behalf of the Collaboration.

To safeguard the integrity of the main trial, reports of any satellite studies will not be submitted for publication without prior discussion with the Project Management Group.

Once the main report has been published, a lay summary will be sent to participants who have indicated they would like to receive one.

APPENDICES

kat

Knee Arthroplasty Trial

INFORMATION SHEET & LETTERS FOR GENERAL PRACTITIONERS

LETTER LETTING GPs KNOW THAT A PATIENT HAS BEEN APPROACHED¹

Dear

KNEE ARTHROPLASTY TRIAL

The NHS R&D Programme is evaluating developments in knee replacement surgery in a large national trial (The knee arthroplasty trial or KAT, for short).

Your patient, (patient name, DOB), is being considered for recruitment to the KAT study. Recently s/he has been sent information about the study, describing the trial options for which s/he is likely to be eligible.

We enclose a brief outline of the study for your information. We realise that s/he may make an appointment to discuss whether or not to take part in the trial and we hope this information will be useful then.

Involvement of your patient in the trial would not mean any significant work for you. All data for the study will be collected from hospital case notes and by patient completed questionnaire.

Yours sincerely

KAT Study Nurse

¹ On Kat headed paper with relevant study nurse address

LETTER LETTING GPs KNOW THAT A PATIENT HAS BEEN RECRUITED TO THE TRIAL¹ (GP previously notified of approach)

Dear

KNEE ARTHROPLASTY TRIAL

You may remember that we wrote to you recently describing the KAT Study. Your patient, (patient's name, DOB,) has agreed to join the study.

When s/he has had the operation, you will receive discharge information as usual from your patient's orthopaedic surgeon.

We will carry out follow-up by sending postal questionnaires direct to (patient's name) at three months post-operatively and annually for up to ten years. We would be grateful if you would help us by sticking the label provided on (patient's name)'s notes, contacting [contact]: if the patient changes address, is too ill to complete questionnaires, or dies. Other than that, we should not need to obtain any other information from you.

If you require any further details about the study, please do not hesitate to contact me.

Yours sincerely

KAT Study Nurse

Encl

¹ On Kat headed paper with relevant study nurse address

ALTERNATIVE LETTER LETTING GPs KNOW THAT A PATIENT HAS BEEN RECRUITED TO THE TRIAL¹ (GP not previously notified of approach)

Dear

KNEE ARTHROPLASTY TRIAL

The NHS R&D Programme is evaluating developments in knee replacement surgery in a large national trial (The knee arthroplasty trial or KAT, for short).

Your patient, (patient's name, DOB,) after being sent information about the study and meeting with myself has agreed to take part.

I enclose a brief outline of the study for your information. I have advised (patient's name) to contact myself if s/he has any further questions.

When s/he has had the operation, you will receive discharge information as usual from your patient's orthopaedic surgeon.

We will carry out follow-up by sending postal questionnaires direct to (patient's name) at three months post-operatively and annually for up to ten years. We would be grateful if you would help us by sticking the label provided on (patient's name)'s notes, contacting [contact]: if the patient changes address, is too ill to complete questionnaires, or dies. Other than that, we should not need to obtain any other information from you.

Yours sincerely

KAT Study Nurse

Encl

¹ On Kat headed paper with relevant study nurse address

kat

Knee Arthroplasty Trial

CONSENT FORM

kat

Knee Arthroplasty Trial

**PARTICIPANT QUESTIONNAIRES
& LETTERS**

3 MONTH FOLLOW-UP LETTER TO PARTICIPANT¹

Dear {Participant name}

Thank you for agreeing to take part in the KAT study.

It is now three months since you had your {left/right} knee replacement. We would therefore like to ask you about how your knee replacement is functioning and the medical services you have used since the operation. We have enclosed a questionnaire which we would be delighted if you could complete and return in the pre paid envelope.

We shall contact you again in nine months time (which will be a year following your operation) and then annually after this time, with further questions about your knee replacement.

If you have any questions about this study please do not hesitate to contact us.

We wish you good health and look forward to receiving your questionnaire.

Yours sincerely,

KAT Trial Co-ordinator

Encl

¹ On Kat headed paper with Trial Office address

ONE YEAR FOLLOW-UP LETTER TO PARTICIPANT¹

Dear {Participant name}

Thank you for your continued participation in the KAT study.

It is now a year since you had your {left/right} knee replacement. We would therefore like to ask you about how your knee replacement is functioning and the medical services you have used since your operation. We have enclosed the annual questionnaire which we would be delighted if you could complete and return in the pre paid envelope.

We shall contact you again in a year with further questions about your knee replacement.

If you have any questions about this study please do not hesitate to contact us.

We wish you good health and look forward to receiving your questionnaire.

Yours sincerely,

KAT Trial Co-ordinator

¹ On Kat headed paper with Trial Office address

YEAR TWO - TEN FOLLOW-UP LETTER TO PARTICIPANT¹

Dear «Title» «Surname»

Thank you for your continued participation in the KAT study.

It is now a year since we last contacted you about your «IndexDesc» knee replacement. We would therefore like to ask you about how your knee replacement is functioning and the medical services you have used in the past year. We have enclosed the annual questionnaire which we would be delighted if you could complete and return in the pre paid envelope.

We shall contact you again in a year with further questions about your knee replacement.

If you have any questions about this study please do not hesitate to contact us.

We wish you good health and look forward to receiving your questionnaire.

Yours sincerely,

KAT Trial Co-ordinator

Encl

¹ On Kat headed paper with Trial Office address

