7. OUTCOME ASSESSMENT

Participation does not require any special tests or extra hospital visits (over and above standard care).

Most data describing outcomes will be collected directly from participants through postal questionnaires. The same questionnaire will be completed at three months and then annually (Appendix 5). It will include:

- the Oxford Knee Score (a twelve-item instrument measuring patients' perceptions of pain and function).
- the SF-12 (an abbreviated form of the SF-36, explaining more than 90% of the variance of the SF36).
- the EQ-5D (to derive quality-adjusted life years, QALYs).
- questions about any further hospital admissions and surgery.

Clinical data will be collected in a standardised way from casenotes to describe operative complications, and any further surgery, especially for revision.

Participants will be flagged at the Office for National Statistics for notification of death registration (and possible later tracing if contact has been lost during follow-up).

Follow-up is planned for at least ten years.

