Differences between the groups in revision rates might bias comparisons of the Oxford scores. For this reason these analyses will be run in two ways: firstly on the actual scores at a particular time, irrespective of further surgery (aiming to compare the clinical policies actually used, including repeat surgery); and second, after imputing a score for those who had revision surgery (aiming to compare the initial surgery used in the trial). Although patient survival will be a measure of outcome and described in trial reports, most analyses will be based on the assumption that the alternative prostheses do not have differential effects on mortality. Analyses of the Oxford score will principally be based on survivors but possible effects of excluding those who died will be explored using imputed scores based on the data available. In respect of the revision analyses, participants will be assumed to be at risk only when alive, using a multi-decrement life table approach. It is difficult to predict the proportion of participants who will die or be lost to follow-up, but allowance has been made by aiming to recruit at least 1500, 750 and 400 as applicable.

Additional analyses, stratified by surgeon, will explore any effects of make of prosthesis, surgical experience (‘the learning curve’) and rehabilitation policy.

Timing and frequency of analyses and reporting

Two principal analyses are planned - at six years and then at twelve years.

By six years, participants will have had a median of four years follow-up (assuming it takes six months to initiate the trial, two years to recruit all patients, and six months to complete and report analyses). By this stage, data on early complications, which are likely to be mainly medical, will be available. There will be some early failures, for example due to infection. Outright device failure will be uncommon, but differences in functional scoring could be apparent.

By twelve years, follow-up will have been for a median of ten years. A substantially larger number of device failures and subsequent revisions will have occurred by then.

Confidential interim analyses will be performed at other times as requested by the Data Monitoring Committee, which is expected to meet at least annually (see below).

Economic evaluation

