3 MONTH FOLLOW-UP REMINDER LETTER TO PARTICIPANT¹

Dear {Participant name}

Thank you for agreeing to take part in the KAT study. Your help is very important in finding out how best to help people with knee replacements like the one you received. We greatly appreciate your interest and help with this trial and would very much like to keep in touch with you.

We recently sent you a questionnaire asking about how your {left/right} knee replacement is functioning and the medical services you have used since your operation. To date, we do not appear to have received your questionnaire. We are really interested in your views and we would be most grateful if you could spare a few minutes of your time to complete the questionnaire and return it to us in the pre paid envelope (I have enclosed another copy of the questionnaire). Please be assured that the information you give will be treated with the strictest confidence. If you have any worries or questions, please do not hesitate to contact me at the Kat Office in Aberdeen ([name]). If you do not wish to complete the questionnaire, please return it blank in the pre paid envelope.

We wish you good health and look forward to hearing from you. Thank you once again for your help.

Yours sincerely,

KAT Trial Co-ordinator

Encl

¹ On Kat headed paper with Trial Office address

ANNUAL FOLLOW-UP REMINDER LETTER TO PARTICIPANT¹

Dear {Participant name}

Thank you for agreeing to take part in the KAT study. Your help is very important in finding out how best to help people with knee replacements like the one you received. We greatly appreciate your interest and help with this trial and would very much like to keep in touch with you.

We recently sent you a questionnaire asking about how your {left/right} knee replacement is functioning and the medical services you have used in the last year. To date, we do not appear to have received your questionnaire. We are really interested in your views and we would be most grateful if you could spare a few minutes of your time to complete the questionnaire and return it to us in the pre paid envelope (I have enclosed another copy of the questionnaire). Please be assured that the information you give will be treated with the strictest confidence. If you have any worries or questions, please do not hesitate to contact me at the Kat Office in Aberdeen ([name]). If you do not wish to complete the questionnaire, please return it blank in the pre paid envelope.

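### From year two the follow-up letters ask only about the past year, so a skipped annual form leaves a gap in self-reported re-admission and revision that no later letter reopens

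*Protocol*

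**What the plan says.** All references are to the protocol; no SAP is at hand.

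- **Source of outcome data.** Section 7 states: "Most data describing outcomes will be collected directly from participants through postal questionnaires". The questionnaire includes items on further admissions and surgery, with no recall window given. The Summary, under Data collection, describes the health-service questions as covering re-admissions and revision surgery.
- **Early letters (Appendix 5).** The three-month letter asks about services used since the operation. The one-year letter asks about "the medical services you have used since your operation".
- **Later letters (Appendix 5).** The letter for years two to ten opens with "It is now a year since we last contacted you about your" knee replacement and asks about "the medical services you have used in the past year". The annual reminder asks about "the medical services you have used in the last year".
- **Second source for revisions.** Section 7 has casenotes used for further surgery, revision in particular. Section 9 has study nurses collect subsequent admissions and help with tracing. Section 10 has co-ordinating nurses help secure complete data after later admissions. Section 12 (Economic evaluation) sends all in-patient admissions for revision through the research nurse system.
- **Risk set.** For the revision analyses, Section 12 says "participants will be assumed to be at risk only when alive, using a multi-decrement life table approach".
- **Loss to follow-up.** Section 12 says "It is difficult to predict the proportion of participants who will die or be lost to follow-up" and makes allowance through the recruitment target.

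**The concern.** The first two letters are cumulative: a participant who misses the three-month form is asked at one year about everything since surgery. From year two this property is lost. The window is one year, and it starts from the Trial Office's last contact, whether or not that contact produced a reply. Someone who does not return year 4 but returns year 5 is prompted about year 5 only. No catch-up question is shown.

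Revision feeds the prosthesis survival curves and sets parameters in the economic model (Section 12), and Section 12 expects most device failures between the six-year and twelve-year analyses. These are the years in which the narrow window applies. Missed revisions would lower the observed rates in every group. If non-response were related both to having a failed knee and to allocation, they would also bias the comparison, although nothing in the protocol shows that this would happen.

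**Working it through.** **1. The recall windows side by side**

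| Contact | Window for services used | Reaches back over a missed form? |
|---|---|---|
| Three-month letter | since the operation | not applicable |
| One-year letter | since the operation | yes |
| Year two to ten letter | past year, from last contact | no |
| Annual reminder | last year | no |

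The gap in self-report follows from the text of the letters. Whether it becomes a gap in the revision data depends on the casenote and nurse route.

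**2. The plan's own power figures for revision**

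Inputs from Section 12: patellar resurfacing (comparison B), 700 per group, 10% versus 5%, stated power above 90%; uni-compartmental arthroplasty (comparison D), 175 per group, 5% versus 15%, stated power 90%. Two-sided 5% level, which Section 12 states for the OKS calculations and is taken to apply here.

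Method: power = Φ[(d − 1.96·se0)/se1], with se0 = √(2·p̄(1−p̄)/n) and se1 = √((p1(1−p1)+p2(1−p2))/n).

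- B: d = 0.05, p̄ = 0.075, se0 = 0.01408, se1 = 0.01402. (0.05 − 0.02759)/0.01402 = 1.599, so power is 94.5%. The stated figure reproduces.
- D: d = 0.10, p̄ = 0.10, se0 = 0.03207, se1 = 0.03162. (0.10 − 0.06286)/0.03162 = 1.175, so power is 88.0%, close to the stated 90%.

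**3. From non-response to missed revisions**

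The protocol gives neither a non-response rate nor the share of revisions that casenotes and nurses would miss. Both are assumed here. If q is the annual non-response and u the share the other sources miss, the missed fraction is f = q × u. With q = 20%:

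- u = 10%: f = 0.20 × 0.10 = 2%
- u = 50%: f = 0.20 × 0.50 = 10%
- u = 100% (the other sources catch nothing): f = 20%

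**4. Effect on power**

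Each rate is multiplied by (1 − f), equally in both arms.

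| f | B rates | B power | D rates | D power |
|---|---|---|---|---|
| 0 | 10% v 5% | 94.5% | 15% v 5% | 88.0% |
| 2% | 9.8% v 4.9% | 94.1% | 14.7% v 4.9% | 87.3% |
| 10% | 9% v 4.5% | 91.9% | 13.5% v 4.5% | 84.0% |
| 20% | 8% v 4% | 88.4% | 12% v 4% | 79.0% |

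For the assumed q, these overstate what rewording could recover, for two reasons. First, q includes people who never reply again, and a wider window reaches only those who skip a form and later return one. Second, f is applied to the whole long-term rate, although the one-year letter already covers the first year in full.

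**The case against.** The strongest reply is that revisions do not depend on the postal form. Casenotes are named specifically for revision, admissions for revision surgery go through the research nurses, and unreturned forms prompt reminders and phone calls (Section 11). Section 12 uses the annual questions for primary care, out-patient and other service counts, for which a one-year window is right. This stands, and it limits the size of the problem. It does not remove it, because the protocol does not say how a nurse would learn of an admission to a hospital outside the trial. The GP letters ask GPs to report only a change of address, illness that prevents completion, or death.

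A second reply is that the letters are only cover notes. The questionnaire is not in the text available, and its surgery items may reach further back. That also stands; if they do, only the letters need to be brought into line.

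A reader might further infer that living non-responders are always counted as at risk, so that missed revisions are scored as implant survival. The documents do not support this. "participants will be assumed to be at risk only when alive, using a multi-decrement life table approach" removes time after death; being alive is a necessary condition for being at risk, not a sufficient one. No exit for loss to follow-up is stated, but that detail commonly sits in an SAP, so its absence is not an error here. Nor do the documents support saying that revisions are found mainly by post, or that 10% to 30% of them would be missed.

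**Conclusion.** The point holds in a narrow form. From year two the letters stop covering time missed since the last returned form, and a revision in a skipped year is lost if casenotes and nurses also miss it. The gap in the letters is certain; its effect on the revision data is unknown. With an assumed 20% non-response, 2% to 10% of revisions would be missed as the other sources miss a tenth to a half. Comparison B then keeps 94.1% to 91.9% power, still above the stated 90%, and comparison D falls from 88.0% to 87.3% or 84.0%. These figures assume equal loss in both arms and no wider window in the questionnaire, and the part that rewording recovers is smaller. The point is worth correcting because the change is trivial and a revision not asked about may be hard to trace years later.

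**What to change.** In the year two to ten letter, the annual reminder and the matching questionnaire item, ask about any surgery on the replaced knee since the original operation, with date and hospital. Alternatively, print the date of the last returned form and ask about the time since then. Keep the one-year window only for GP, out-patient and other service counts.

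As a secondary clarification, add a sentence to Section 12 (or confirm it in the SAP) that revision follow-up is censored at the last date on which revision status is known.

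The cost is a reworded sentence in each of two letters, one questionnaire item and one sentence on censoring. The downside is longer recall for a rare, memorable event, and possible repeat reports of the same operation, which the date and hospital would identify.
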